3.0 PRETREATMENT EVALUATION

Evaluations Required for Eligibility:

1. Complete history & physical examination
2. Assessment of performance status
3. Serum PSA (<90 days prior to registration)
4. Pathologic confirmation of adenocarcinoma of the prostate
5. Bone scan (PSMA PET can be substituted for bone scan)
6. Ultrasound of prostate, MRI or CT of pelvis
7. Endorectal/Multi parametric MRI
8. Patient questionnaires (see appendix VI).
 - 1 Expanded Prostate Cancer Index Composite (EPIC)-26 questionnaire
 - EuroQol EQ-5D-5L

4.0 RADIATION THERAPY

DE-SBRT will be delivered using the CyberKnife robotic radiosurgery system. Patients will be treated with five SBRT treatments (8 Gy per fraction to the PTV, and 9-10 Gy per fraction to any nodules identified on endorectal MRI) over 7-10 days.

1 MARKER/SPACE OAR PLACEMENT

All patients will have fiducial markers placed in the prostate prior to treatment planning. At least three fiducial markers or electromagnetic transponders will be placed under transrectal ultrasound guidance, using either transperineal or transrectal approach, with local anesthesia and/or sedation as required. At least three markers must be usable for tracking during treatment. Space OAR hydrogel is a spacer providing space between the rectum and the prostate, making it much less likely that the rectum is exposed to high dose radiation must be utilized in all patients undergoing treatment.

2 TREATMENT PLANNING IMAGING AND CONTOURING STRUCTURES

To allow marker stabilization and resolution of swelling, planning studies will be imaged > 7 days after placement. Immobilization devices will be used as needed. CT scans will be taken for treatment planning. Planning MRI images will be obtained simultaneously with CT images and are utilized for treatment planning.

The structures listed below will be contoured on the CT scan and evaluated with DVH analysis. Bowel peristalsis and bladder filling change the size and location of normal structures. For treatment plans utilizing MRI, if the CT and MRI show normal tissues in different locations immediately adjacent the prostate, the contoured structure shall be a larger composite of both image sets.

1. Rectum: For this study, the rectum is defined as the solid structure, including the lumen and rectal wall, extending from the level of the ischial tuberosity to the sigmoid flexure.
2. Bladder: For this study, the bladder is defined as a solid structure including the bladder wall and lumen.
3. Femoral heads: For this study, the femoral heads are defined as the femoral head and neck.
4. Sigmoid colon or other bowel: Bowel lying within 2 cm of the PTV should be contoured. For non-isocentric treatment plans, distal hot spots need to be avoided.
5. Prostatic urethra: For this study, the prostatic urethra is defined as the lumen-mucosal interface, extending from bladder neck to the membranous urethra.

6. Membranous urethra: For this study, the membranous urethra is defined as the lumen-mucosal interface, extending from the prostatic apex to the penile bulb.
7. Penile Bulb: For this study, the penile bulb is defined as the portion of the bulbous spongiosum that lies inferior to the urogenital diaphragm.
8. Bladder Neck: For this study, the bladder neck is defined as the most proximal portion of the bladder extending from the prostate base and urethral junction.

3 SBRT:

SBRT delivery:

The protocol requires image guidance via radio-opaque fiducial markers or electromagnetic transponders implanted in the prostate. At least three fiducial markers must be identified for each treatment. If fewer than three can be tracked, then additional fiducial markers will be placed, and the patient re-planned. Live fiducial tracking is required. No rectal balloons are allowed.

Dose specifications:

Patients will receive five SBRT treatments of 8 Gy each. The total dose will be 40 Gy. The five treatments will be completed in 7-10. A minimum of 20 hours should elapse between treatments. The total duration of treatments should take no longer than 10 days.

Target Volumes:

Gross Tumor Volume (GTV): The GTV shall include the prostate and any gross extension. 2cm of the SV will be contoured separately. Malignant Nodules identified on MRI will be contoured separately.

Planning Tumor Volume (PTV): The prescription dose (8 Gy) shall be delivered to the PTV. The PTV shall equal the CTV expanded 3 mm in all other directions. Any malignant nodules identified on endorectal/Multi parametric MRI will be prescribed an integrated boost of 10Gy per fraction while respecting all dose constraints. (9 Gy per fraction will be considered an acceptable variation if dose constraints cannot be met.) The PTV-SV will receive 7.25 Gy per fraction.

SBRT Dose Specifications:

PTV: The prescription dose of 40 Gy shall be the dose to the PTV: Per protocol, the volume of the PTV receiving 40 Gy (V40 Gy) shall be at least 95%. The PTV-SV will be treated to 36.25 Gy and the PTV-SV receiving 36.25 Gy shall be at least 95%.

Rectum: Per protocol, the volume of the rectum receiving 36 Gy (V36 Gy) shall be < 1cc. The rectal dose-volume histogram (DVH) constraints are < 50% rectal volume receiving 50% of the prescribed dose, < 20% receiving 80% of the dose, < 10% receiving 90% of the dose, and < 5% receiving 100% of the dose

Bladder: Per protocol, the volume of the bladder receiving 40Gy (V40 Gy) shall be < 5 cc. Although not required, the bladder dose-volume histogram (DVH) goals are < 40% bladder volume receiving 50% of the prescribed dose, < 10% receiving 100% of the dose.

Bladder Neck: Per protocol, the maximum dose (0.03 cc) to the bladder neck should be \leq 40 Gy.

Sigmoid colon and other bowel: Per protocol, the volume of the sigmoid colon and other bowel receiving 36 Gy (V36Gy) shall be < 1cc.

Prostatic urethra: Per protocol, the maximum dose (0.03 cc) to the prostatic urethra should be < 43 Gy.

Membranous urethra: Per protocol, the maximum dose (0.03 cc) to the membranous urethra should be < 43 Gy.

Penile bulb: Per protocol, the volume of the penile bulb receiving 35 Gy (V35Gy) shall be < 50%. Minor variations: V35Gy \geq 50%, but < 75%. Major variations: V35Gy > 50%.

5.0 ANDROGEN SUPPRESSION

Androgen suppression (ADT) consists of LHRH agonist for a total of 6 months for unfavorable intermediate risk patients and 18 months for high and very high-risk patients. The choice of LHRH agonist is at the discretion of the treating physician. ADT should proceed initiation of SBRT however there is no minimum interval of ADT prior to initiation of SBRT which is patient/physician defined but should not exceed 6 months.

Risks of Androgen Suppression

ADT has several reported adverse and serious adverse reactions that have been reported in patients with advance prostate cancer who received Orgovyx (ADT oral use tablets). The most common adverse reactions hot flush, musculoskeletal pain (including arthralgia, back pain, pain in extremity, musculoskeletal pain, myalgia, bone pain, neck pain, arthritis, musculoskeletal stiffness, non-cardiac chest pain, musculoskeletal chest pain, spinal pain, and musculoskeletal discomfort), fatigue, diarrhea, and constipation.

Serious adverse reactions occurred in 12% of patients who received ADT. Serious adverse reactions in \geq 0.5% of patients included myocardial infarction (0.8%), acute kidney injury (0.6%), arrhythmia (0.6%), hemorrhage (0.6%), and urinary tract infection (0.5%). Fatal adverse reactions occurred in 0.8% of patients receiving ADT including metastatic lung cancer (0.3%), myocardial infarction (0.3%), and acute kidney injury (0.2%). Fatal and non-fatal myocardial infarction and stroke were reported in 2.7% of patients receiving Orgovyx.

6.0 PATIENT ASSESSMENTS

| Assessment | Pre-entry | | | | Follow-up interval: months post therapy | | | | |
|----------------------------|-----------|---|---|---|---|----|----|-------|---|
| | | 1 | 3 | 6 | 12 | 18 | 24 | 36-60 | |
| History (SHIM, AUA) | X | | X | X | X | X | X | | X |
| Physical exam (DRE) | X | | | X | X | X | X | | X |
| ECOG Performance Scale | X | | | X | X | X | X | | X |
| Prostate Biopsy | X | | | | | | | | |
| PSA | X | | | X | X | X | X | | X |
| Prostate volume assessment | X | | | | | | | | |
| Bone scan | X | | | | | | | | |
| Pelvic imaging | X | | | | | | | | |
| Toxicity evaluation (AUA) | X | | X | X | X | X | X | | X |
| EPIC-26 Questionnaire | X | | | | X | X | | X | X |
| EuroQol EQ-5D-5L | X | | | | X | X | | X | X |

Assessment schedule: Quality of life measurements will take place per the table, then annually through 5 years post-treatment.

7.0 CLINICAL ENDPOINTS:

Patients will have toxicity evaluation weekly during treatment. At 1 month following treatment, patients will be assessed for acute toxicity. At 6, 12, 18, and 24 month intervals (and every year thereafter, through year 5- 10, if investigators opt to continue past year 5), patients will be seen and evaluated, including a history, physical exam, performance status, PSA, toxicity evaluation. In addition, at 6 months, 12 months and annually thereafter, EPIC-26 will be administered. Examination and studies may be done at outside facility. Prostate biopsy, bone scan (PSMA PET/CT may be substituted for bone scan) and pelvic MRI will be performed at time of biochemical or clinical failure.

Criteria for toxicity:

Acute side effects (<=90 days of treatment start) and late side effects (> 90 days of treatment start) will be assessed using the NCI Common Toxicity Criteria version 4.0 (see appendix V).

Criteria for disease control:

1. Biochemical disease free survival (bDFS):
 - a. Phoenix definition (55): failure occurs when the PSA is ≥ 2 ng/ml more than the lowest PSA measurement before the current one, with no backdating. Administration of salvage therapy will be considered failure.
2. Duration of local control: clinical evidence of local progression or recurrence. Clinical failure includes a palpable abnormality that has increased in size, failure of regression of a palpable abnormality by 2 years after treatment, or redevelopment of a prostate abnormality after complete response. Patients with a prostate abnormality compatible with local recurrence, or a PSA failure shall undergo a prostate biopsy. Histologic criteria for local failure is a positive prostate biopsy more than 2 years after treatment. Patients

with a normal exam and no evidence of PSA failure shall be considered controlled locally. Patients with clinical failure and no biopsy are considered local failures. If a patient is locally controlled at the time of orchiectomy or androgen ablation, he is censored and considered “not evaluable” for further local control.

3. Distant failure (includes regional failure): documented if clinical, bone scan, CT or other imaging study shows metastatic disease. Biochemical failure with a negative prostate biopsy shall be considered distant only failure. Biopsy of metastatic site required if radiographic or clinical findings are equivocal. Type of metastatic failure (distant and/or regional) shall be recorded if known. Prostate biopsy recommended at this time.
4. Disease-free survival: for any measure of disease, including PE, PSA, bone scan, CT/MRI and biopsy, or death.
5. Disease-specific survival: for any of the following: Death due to prostate cancer. Death due to other causes, with active malignancy (defined by clinical or biochemical evidence of progression). If a patient suffered a previous relapse, but has inactive disease, this is not considered a disease-specific death. Death due to complications of treatment.
6. Overall survival: for death from any cause.

Quality of Life/Health Outcomes instruments (See Appendix VI):

1. Disease-specific quality of life: The **Expanded Prostate Cancer Index Composite (EPIC)-26** is a validated comprehensive instrument developed to assess patient function and bother after prostate cancer treatment. It was developed by an expert panel of urological oncologists, radiation oncologists, survey researchers, and prostate cancer nurses, to address symptoms related to radical prostatectomy, radiotherapy, and hormonal symptoms.

Quality-Adjusted Life Years (QALY): **EuroQol EQ-5D-5L** is a validated instrument which provides a single index value for a patient’s overall health status (otherwise known as “utility”). It is widely used in cancer clinical trials (56, 57). Five of the items are scored on a 3-point Likert scale (mobility, ability for self-care, ability to perform usual activities, pain/discomfort, anxiety/depression), and one item assesses a patient’s overall health state on a visual analog scale ranging from 0 (worse imaginable state) to 100 (best imaginable).

8. STATISTICAL CONSIDERATIONS:

Endpoints:

Primary Endpoint

1. **Toxicity** will be assessed using the NCI Common Toxicity Criteria version 4.0.

Secondary Endpoints

1. **Biochemical disease-free survival (bDFS)** will be defined as the time in months from completion of SBRT to biochemical failure. Patients who are free from biochemical failure on the date of closing follow-up will be censored on that date. The Phoenix definition will be used to assess biochemical failure as described in Section 10.
2. **Duration of local control** will be defined as the time in months from SBRT completion to local failure.
3. **Distant failure (includes regional failure)** will be defined as the time in months from SBRT completion to distant failure.
4. **Disease-free survival** will be defined as the time in months from the date that the patient is determined to be free of disease to the date of known disease recurrence for any measure of disease. Patients who are alive and free from disease recurrence on the date of closing follow-up will be censored on that date.
5. **Disease-specific survival** will be defined as the time in months from completion of SBRT to death due to prostate cancer, other causes with active malignancy, or complications from treatment. Patients who are alive or dead with disease relapse but with inactive disease on the date of closing will be censored on that date.
6. **Overall survival** will be defined as the time in months from SBRT completion until death. Patients who are alive on the date of closing will be censored on that date.
7. **Quality of life**

Study Design:

The target sample size is 100 patients for this Phase II study. Allowing for a 15% ineligibility rate, the total sample size is 115 patients. Accrual is anticipated to be completed within 5 years of institutional IRB approval. This Phase II trial will provide information to guide future Phase III studies. Sample size determination is based on the late toxicity endpoint. A single-stage Fleming design will be used to test the null hypothesis that the late unacceptable radiation toxicity probability at 2 years p is < 0.05 versus the alternative hypothesis that toxicity probability at 2 years is > 0.15 . Unacceptable toxicity will be defined as grade 3 or higher toxicity. If 10 or fewer patients experience late radiation toxicities at 2 years, the null hypothesis will not be rejected and then the regimen will be considered for a phase III study. If at least 10 patients experience late radiation toxicities at 2 years, the null hypothesis will be rejected. This design has a power of 89% and a type I error rate of 0.10.

Analysis Plan

1. Number and percentage of subjects for each toxicity will be summarized overall by body system and by onset time (acute: ≤ 90 days of treatment start and late: >90 days of treatment start). The tabulation will also be separated by toxicities of Grade 3 and above.
Future studies incorporating DE-SBRT would be worthwhile if the rate of grade 3 GU/GI toxicity was $\leq 10\%$.
2. Biochemical disease-free survival, disease-free survival, disease-specific and overall survival curves will be calculated and presented by the methods of Kaplan and Meier.
3. The proportion of patients with local and distant failure will be reported with a 95% binomial confidence interval.
4. General health related and disease specific quality of life measurements will be summarized over time. Graphical displays will be created for each patient's trajectory over time and also summarized using the average for all patients.

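### The site-of-failure rules count every PSA failure with a negative biopsy as distant, whatever the imaging shows, and leave some PSA-only failures with no site at all

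*Protocol*

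**What the plan says.** The rules are in Section 7.0 of the protocol, under the criteria for disease control, items 2 and 3.

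- **Biopsy trigger:** "Patients with a prostate abnormality compatible with local recurrence, or a PSA failure shall undergo a prostate biopsy". No time limit is attached.
- **Histologic local failure:** "Histologic criteria for local failure is a positive prostate biopsy more than 2 years after treatment".
- **Clinical local failure:** "Clinical failure includes a palpable abnormality that has increased in size, failure of regression of a palpable abnormality by 2 years after treatment", and also a prostate abnormality that reappears after complete response. Further: "Patients with clinical failure and no biopsy are considered local failures".
- **Local control:** patients "with a normal exam and no evidence of PSA failure shall be considered controlled locally".
- **Distant failure, documented route:** "documented if clinical, bone scan, CT or other imaging study shows metastatic disease". Equivocal findings require a biopsy of the metastatic site.
- **Distant failure, assigned route:** "Biochemical failure with a negative prostate biopsy shall be considered distant only failure".

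The opening paragraph of Section 7.0 orders a prostate biopsy and a bone scan (or PSMA PET/CT) at failure, and adds that "pelvic MRI will be performed at time of biochemical or clinical failure".

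Local control and distant failure are part of the primary objective in Section 2.0 and are secondary endpoints in Section 8.0. The analysis plan in Section 8.0 reports both as proportions with 95% binomial confidence intervals.

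**The concern.** Two things go wrong when the rules are applied as written.

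First, distant failure has two standards of evidence. Equivocal signs of metastasis need tissue. A PSA failure with clearly negative imaging needs nothing beyond a negative prostate biopsy to count as distant. A negative biopsy does not show where the PSA comes from, and it may have missed a local recurrence.

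Second, the rules do not cover every PSA failure. Biopsy is triggered at any time, but a positive result meets the histologic criterion only after 2 years. No default is given for a PSA failure in which the biopsy is not done.

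At stake are two reported proportions that describe where the regimen fails. Section 1.0 calls the boost to the MRI-defined nodule the experimental element, so readers will look at the split between local and distant failure. That split would partly reflect the assignment rules rather than observed disease.

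**Working it through.** The protocol gives no expected local or distant failure rate and no biopsy accuracy, so there is no stated figure to reproduce. The check is mainly logical.

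**1. Can PSA failure occur before 2 years?** Section 7.0 schedules PSA at 6, 12, 18 and 24 months. The Phoenix rule as written (2 ng/ml above the lowest prior value) has no minimum time. So biopsies for PSA failure at or before 2 years are foreseen.

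**2. Classification of a PSA failure with normal exam and no local or metastatic finding on imaging:**

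| Biopsy | Category under Section 7.0 |
|---|---|
| Positive, more than 2 years | Local failure |
| Positive, at or before 2 years | None |
| Negative, any time | Distant only |
| Not done | None |

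In the second row the man is too early for the histologic criterion, has no clinical evidence of local failure, does not meet the stated condition for local control because his PSA has failed, and is not distant because his biopsy is not negative. The censoring rule at androgen ablation does not settle his case, since it applies to men who are locally controlled. Section 8.0 adds only the time origin and the reporting format.

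**3. Direction.** The early-positive row takes biopsy-proven disease out of the local count while leaving the man in the denominator. The no-biopsy row does the same for any local recurrence in that group. The negative-biopsy row raises distant failure above what is documented, and moves a local recurrence missed by biopsy from local to distant.

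**4. Illustration in 100 patients; every input except the 100 is an assumption.** Let B be the number of PSA failures with normal exam and negative imaging, all biopsied; f the share truly local; e the share of true local failures biopsied at or before 2 years; s the biopsy sensitivity.

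- True local = B × f
- Recorded local = B × f × s × (1 − e)
- No category = B × f × s × e
- Recorded distant = B × f × (1 − s) + B × (1 − f)

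With B = 10 to 20, f = 0.3 to 0.5, e = 0.1 to 0.5 and s = 0.7 to 1.0:

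- True local: 10 × 0.3 = 3 to 20 × 0.5 = 10.
- Recorded local: 10 × 0.3 × 0.7 × 0.5 = 1.05 to 20 × 0.5 × 1.0 × 0.9 = 9.
- No category: 10 × 0.3 × 0.7 × 0.1 = 0.21 to 20 × 0.5 × 1.0 × 0.5 = 5.
- True local recorded as distant: 0 (s = 1) to 20 × 0.5 × 0.3 = 3.
- Recorded distant: 10 × 0.5 = 5 (s = 1) to 20 × 0.3 × 0.3 + 20 × 0.7 = 1.8 + 14 = 15.8. None of these men has metastasis on imaging.

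**5. Relative size and precision.** One or two unclassified men in 100 change an assumed local failure rate of 3% by 33 to 67% in relative terms (1/3, 2/3), of 5% by 20 to 40% (1/5, 2/5), and of 10% by 10 to 20% (1/10, 2/10). The exact 95% interval for 5/100 is 1.6% to 11.3%, so a shift of 1 to 2 points lies within sampling error. Unlike sampling error, the effect of each rule is systematic.

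**The case against.** Several points on the other side have weight.

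- **Imaging is required.** A reader might infer that men are called distant failures without any imaging. Section 7.0 orders the imaging at failure. What stands is that the negative-biopsy rule does not depend on its result.
- **Not every early positive biopsy is unclassified.** Item 2 opens with clinical evidence of local progression or recurrence, and its list of clinical failures is not exhaustive. A recurrence seen on MRI can be read as local failure, palpable progression is local, and imaged metastasis is distant. The gap is confined to PSA failures with none of these.
- **The 2-year limit may be deliberate.** The same item allows 2 years for a palpable abnormality to regress. The document does not show that an early positive biopsy is a true failure, so it would go too far to call the limit an error. What is missing is the category for these men.
- **Net bias.** A reader might infer that the rules as a whole bias local failure downward in favour of the regimen. The documents do not support that: clinical failure without biopsy and non-regression by 2 years both count as local and push the rate up. A higher distant-failure proportion also makes the regimen look worse, and the hypothesis in Section 2.0 concerns biochemical control.
- **Consequence.** Section 8.0 sets no test or threshold on site of failure; sample size and the decision on a phase III study rest on toxicity.

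These points narrow the concern. They do not close the gap or justify counting imaging-negative men as distant failures.

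**Conclusion.** The point holds in limited form. As written, the rules put PSA failures with no evidence of metastasis into the reported distant-failure proportion. They also give no site to a PSA failure with normal exam and negative imaging whose biopsy is positive at or before 2 years, or who has no biopsy. Taken alone, these two features raise distant and lower local failure. The net bias in the local rate is uncertain, and its size cannot be derived from the protocol; the ranges above rest on assumed inputs, and the true effect may be small.

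The men concerned still count as failures for biochemical disease-free and disease-free survival, and the toxicity-based sample size is untouched. The change is still worth making, because these are stated endpoint definitions and the data needed to apply better ones are already required.

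**What to change.** Amend items 2 and 3 of the disease-control criteria in Section 7.0, and the matching analysis item in Section 8.0:

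1. Count as distant failure only metastatic disease documented clinically, by imaging or by histology. Report PSA failure with negative biopsy and negative imaging separately, as biochemical failure with site not established.
2. Assign a category to PSA failure with a positive biopsy at or before 2 years. Report the local-failure proportion twice: with these men counted as local failures, and under the existing 2-year criterion.
3. Place PSA failure with no biopsy and no clinical or imaging finding in the site-not-established category.

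The cost is a few sentences and one more row in the table of failures. No new procedures are needed. The local-failure rate that counts early positive biopsies may be slightly less favourable. Settling this before failures accumulate avoids case-by-case decisions once results are known.

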No Nodal or Distant Metastases documented on CT or MRI of the pelvis and bone scan (PSMA PET/CT may be substituted for bone scan).

Unfavorable Risk Prostate Carcinoma as Described is documented.

No prior pelvic radiotherapy.

No prior TURP.

Prostate volume < 100 cc

AUA score < 20

No recent (within 5 years) or concurrent cancers other than non-melanoma skin cancers.

Patient must have no medical or psychiatric illnesses that would interfere with treatment or follow-up.

No implanted hardware adjacent to the prostate that would prohibit appropriate treatment planning and treatment delivery is allowed.

Patient must speak and comprehend the English language to complete questionnaires.

Patient's with very high risk prostate cancer must be seen in consultation by medical oncology as per NCCN guidelines version 4.2022 for consideration for abiraterone or docetaxel following radiation.

ELIGIBILITY CHECKLIST

(Y) 1. Is there histologically confirmed adenocarcinoma of the prostate within 360 days of enrollment?

2. What is the Gleason score?

3. What is the T stage?

(N0 or Nx) 4. What is the N stage?

(M0 or Mx) 5. What is the M stage?

(ng/ml) 6. What is the PSA (< 90 days prior to registration)?

(N) 7. Has the patient had prior pelvic radiation?

(N) 8. Has the patient had a TURP?

(< 100 cc) 9. Is the prostate volume < 100 cc?

(N) 10. Has the patient had previous (within the last 5 years) or concurrent cancer other than basal cell or squamous cell skin cancer?

(N) 11. Are there any major medical or psychiatric illnesses which would prevent the completion of treatment or interfere with follow-up?

(Y) 12. Has the patient signed a study-specific consent form?

(AUA < 20) 13. Is the patient's AUA score < 20?

(N) 14. Does the patient have implanted hardware adjacent to the prostate that would prohibit appropriate treatment planning and treatment delivery?

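### The local-control rule censors at androgen ablation without limiting this to salvage, although Section 5 assigns androgen suppression to every risk class before SBRT

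*Protocol*

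**What the plan says.** Four parts of the protocol bear on this point.

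- **Section 7.0, Criteria for disease control, item 2 (Duration of local control).** "If a patient is locally controlled at the time of orchiectomy or androgen ablation, he is censored", and he is then "considered “not evaluable” for further local control". The same item describes local control as a normal examination without PSA failure. Item 1, on biochemical disease-free survival, names salvage therapy and counts it as failure. Item 2 does not use the word salvage.
- **Section 5.0, Androgen Suppression.** On assignment and duration: "Androgen suppression (ADT) consists of LHRH agonist for a total of 6 months for unfavorable intermediate risk patients and 18 months". The longer duration applies to the two higher risk classes. On timing: "ADT should proceed initiation of SBRT however there is no minimum interval of ADT prior to initiation of SBRT", where the verb is evidently meant as precede. The lead is not to exceed 6 months.
- **Patient Eligibility.** The entry condition is "Unfavorable Risk Prostate Carcinoma as Described is documented". The Introduction defines three such classes (unfavorable intermediate, high, very high), and Section 5.0 gives each a duration of suppression.
- **Section 8.** Duration of local control "will be defined as the time in months from SBRT completion to local failure". The definition adds no censoring text. The Analysis Plan leaves local control out of its Kaplan-Meier list and reports local failure as a proportion with a 95% binomial confidence interval.

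**The concern.** The event that ends a man's local-control follow-up is described in words that fit a treatment the protocol assigns to every participant, normally begun before the clock starts. A rule of this kind suits a trial in which androgen deprivation is given only after recurrence. Here it collides with the treatment section unless protocol suppression is exempted, and no exemption is written.

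At stake is whether the local-failure figure can be coded in one way. Two people coding the same records could keep or drop the same man. If men are dropped, the loss would not be random, because the rule depends on the findings at examination.

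**Working it through.** No figure in the protocol needs reproducing. The check sets the passages in time order and then illustrates what a smaller denominator would do.

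**1. Who receives suppression.** Only the three unfavorable-risk classes are eligible, and Section 5.0 assigns a duration to each. Every eligible man is therefore assigned suppression.

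**2. Order of events.** Suppression starts, then SBRT starts, then SBRT is completed (time zero). The start of suppression lies before time zero for every man treated as planned.

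**3. How long suppression continues.** Months remaining after SBRT starts = total duration − lead, with a lead of 0 to 6 months.
- Unfavorable intermediate: 6 − 0 = 6, down to 6 − 6 = 0 months.
- High and very high: 18 − 0 = 18, down to 18 − 6 = 12 months.

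SBRT itself takes at most 10 days, so the values counted from completion are almost the same. In high and very-high-risk men, suppression therefore runs through the 6-month visit and to about the 12-month visit or beyond. Examinations are scheduled at both.

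**4. Applying the rule literally, with protocol suppression counted as androgen ablation.** I assume that before SBRT the physical examination decides whether a man counts as locally controlled.
- Normal examination when suppression starts: he meets the condition and is censored before time zero, so he contributes no follow-up.
- Palpable abnormality when suppression starts: he does not meet the condition, so the rule does not apply to him then.
- Abnormality that resolves while suppression continues: he becomes locally controlled during ablation. The text does not say whether the time of ablation means its start or any time while it lasts, so his censoring date is undefined.

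Retention in the endpoint would thus depend on palpability at baseline. The protocol gives no distribution of palpable disease, so the number lost cannot be computed.

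**5. Illustration of precision.** The Analysis Plan does not say whether censored men stay in the denominator of the proportion. With 0 failures among n men, the exact two-sided 95% upper limit is 1 − 0.025^(1/n). The target sample size is 100; the smaller denominators are assumptions.
- n = 100: 1 − 0.025^(1/100) = 3.6%
- n = 50: 1 − 0.025^(1/50) = 7.1%
- n = 20: 1 − 0.025^(1/20) = 16.8%
- n = 0: not estimable

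**The case against.** The best reply is that salvage ablation is the natural reading. The loss of evaluability concerns further local control, which presupposes control already observed after SBRT. The trigger is paired with orchiectomy, which is not part of the regimen. Section 5.0 calls the protocol treatment androgen suppression, not ablation. A reading that defeats the endpoint is unlikely to be the intended one. Local control is secondary in Section 8, and denominator rules are often left to a statistical analysis plan, which is not at hand.

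Most of this stands as evidence of intent. It does not settle the text. The protocol nowhere defines suppression and ablation as different things, and the adjacent biochemical item names salvage where this item does not. The point also goes beyond detail left for later: the protocol states a censoring rule, and on its plain words that rule conflicts with the protocol's own treatment section.

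Two stronger readings are not supported.
- **A reader might infer that no one is evaluable.** That does not follow. The rule applies only to a man who is locally controlled at the time of ablation, and a man with a palpable abnormality at that point is not. The eligible classes include stages above T2a, T3a and T3b, so such men can be expected.
- **A reader might infer that very-high-risk men would be selectively removed by abiraterone after radiation.** The protocol only requires a medical oncology consultation "for consideration for abiraterone or docetaxel following radiation". Neither drug is assigned, the number of men who would receive abiraterone is not given, and the protocol does not say whether it would count as androgen ablation. What remains is that exempting Section 5 suppression alone would leave non-salvage therapy after radiation unclassified.

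**Conclusion.** The concern holds as an unresolved conflict between Section 5.0 and Section 7.0 item 2. On the literal reading, every man with a normal examination when suppression starts is lost from local control before time zero, and the censoring of men whose abnormality resolves on suppression is undefined. On the salvage reading, which is probably the intended one, protocol suppression censors nobody. The effect therefore ranges from none to the loss of many men selected by baseline palpability, and the protocol gives no basis for placing it within that range. The upper limits of 3.6% to 16.8% rest on zero failures and assumed denominators. They show how far the same absence of failures could be reported differently and are not a forecast.

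The reach is limited. Local control is a secondary endpoint in Section 8, although Section 2.0 lists it under the primary objective. Sample size and the decision rule rest on late toxicity and are untouched. The point should be corrected before outcomes are coded, but it does not undermine the design.

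**What to change.** In Section 7.0, Criteria for disease control, item 2:

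1. Restrict the censoring trigger to orchiectomy or androgen deprivation started as salvage for recurrence after SBRT.
2. State that the androgen suppression in Section 5.0 does not trigger it.
3. State whether any non-salvage systemic therapy given after radiation triggers it.

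In the Section 8 Analysis Plan, state whether men censored under this rule stay in the denominator of the local-failure proportion.

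The cost is a few sentences. Only endpoint coding changes: no treatment, visit, data item or sample size is affected.
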